LCRIS	local cutaneous reaction at injection site
MB	major bleeding
MCH	mean corpuscular hemoglobin
MCHC	mean corpuscular hemoglobin concentration
MCV	mean corpuscular volume
MedDRA	Medical Dictionary for Regulatory Activities
Mg	Milligram
mL	Milliliter
MRL	Medpace Reference Laboratories
PD	pharmacodynamic(s)
PK	pharmacokinetic(s)
PT	prothrombin time
QI	25th percentile
Q3	75th percentile
SAE	serious adverse event
SAP	statistical analysis plan
SC	subcutaneous(!y)
Study Drug	ISIS 416858 or placebo
TEAE	treatment emergent adverse event
Tmax	time to maximal concentration
ULN	upper limit of normal
VR	ventricular rate
WBC	white blood cell
WHO	World Health Organization

List of Modifications:

The following modifications have been made to SAP, version 1.0, dated August 20, 2018.

Section	Title	Change
1.3.5	Platelet Function Testing	Details of BCH data added.
2.1	General Overview of Procedures	Blood centers of Wisconsin data added.
2.5.2	Laboratory Data	Clarification of data availability of immunogenicity
3.1.1	General Statistical Methods	visit windows added
3.1.4	Planned Interim Analysis	Added details that no unblinding interim analyses were conducted until final database lock.
3.3.3.3	Bleeding	Added details on minor bleeding summary.

1 INTRODUCTION

This document provides a description of the study organization, study procedures, and the plan for the statistical analysis of the study data. Section 1 discusses study design, objectives, and endpoints; Section 2 provides the study procedures; Section 3 provides the detailed plan for the statistical analyses.

The purpose of this plan is to provide specific guidelines from which the analysis will proceed. Any deviations from these guidelines will be documented in the clinical study report (CSR).

1.1 Study Overview

This is a Phase 2 multicenter, double-blind, randomized, stratified, placebo-controlled study in end-stage renal disease (ESRD) subjects receiving hemodialysis at least 3 times per week for a minimum of 9 hours per week. Subjects will be stratified based on the diagnosis of documented atrial fibrillation (AF) at Screening (Yes/No), enrolled in PK substudy (Yes/No), enrolled in Platelet substudy (Yes/No), and then subjects will be randomized to 1 of 3 dose cohorts in a 1:1:1 ratio (Cohort A, Cohort B, and Cohort C). Within each dose cohort, subjects will be randomized in a 3:1 ratio to receive treatment with Study Drug (either ISIS 416858 or placebo).

Cohort A: 200 mg ISIS 416858 or placebo SC (3:1)

Cohort B: 250 mg ISIS 416858 or placebo SC (3:1)

Cohort C: 300 mg ISIS 416858 or placebo SC (3:1)

All cohorts will consist of up to 4-week screening period for procedures and a 26-week treatment period followed by a 12-week post-treatment evaluation period.

Approximately 204 subjects are planned to be enrolled in parallel in this study.

1.2 Objectives

1.2.1 Primary Objectives

To evaluate the safety, pharmacokinetics (PK), and pharmacodynamics (PD) of ISIS 416858 (200, 250, and 300 mg once weekly) as compared to placebo as assessed by FXI activity reduction in ESRD patients on hemodialysis; [REDACTED]

[REDACTED]

[REDACTED]

1.2.2 Exploratory Objectives

To evaluate the incidence of myocardial infarction (**MI**), stroke, systemic embolism, and cardiovascular mortality.

1.3 Planned Method of Analysis

1.3.J Safety and Tolerability Outcomes

The primary safety outcome is the combination of major bleeding (MB) and clinically-relevant non-major bleeding (CRNMB) during the treatment period (or early study termination).

The safety and tolerability of ISIS 416858 will be accessed by determining the incidence and severity of adverse events (AEs) and will be evaluated by reviewing:

- AEs (including venous thromboembolism (VTE) and bleeding events)
- Vital signs and weight
- ECG
- Physical examination
- Clinical laboratory tests
- Coagulation parameters
- Use of concomitant medications including transfusions

1.3.2 Pharmacodynamic Outcomes

- Change from baseline in FXI antigen and activity
- Change from baseline in activated partial thromboplastin time (aPTT)
- The extent and frequency of clotting on the dialysis filters and circuit

1.3.3 Exploratory Outcomes

- Incidence of myocardial infarction (**MI**), stroke, systemic embolism, and cardiovascular mortality

1.3.4 Other Study Outcomes and Evaluations

- Dialysis adequacy (Urea Reduction Ratio and single pool Kt/v), changes in dialysis prescription (vascular access, time on dialysis, dry weight)
- PK

1.3.5 Platelet Function Testing

For the subgroup of subjects evaluated for platelet function and/or activation, an analysis of pre- and post-treatment results with ISIS 416858 may be conducted overtime and compared to treatment with placebo

1.4 Randomization & Treatment Allocation

Subjects will be randomized on Study Day 1 after all screening assessments have been completed and after the Investigator has verified that they are eligible. No subject may begin treatment prior to randomization and assignment of a unique subject identification number.

All subjects will be randomized using an automated system (IXRS). Subjects will be stratified based on the diagnosis of documented atrial fibrillation (AF) at Screening (Yes/No), enrolled in PK substudy (Yes/No), enrolled in Platelet substudy (Yes/No), and then subjects will be randomized to 1 of 3 dose cohorts in a 1:1:1 ratio (Cohort A, Cohort B, and Cohort C). Within each dose cohort, subjects will be randomized in a 3:1 ratio to receive treatment with Study Drug (either ISIS 416858 or placebo).

1.5 Conduct

The study will be conducted in accordance with current Good Clinical Practice (GCP) and International Conference on Harmonization (ICH) guidelines, the World Medical Association Declaration of Helsinki guidelines, the Food and Drug Administration (FDA) Code of Federal Regulations, and all other local regulatory requirements.

1.6 Data Monitoring

1.6.1 Safety Data Monitoring

Safety data will be monitored as indicated in the ISIS 416858-CSS Medical Monitoring Plan with monthly or more frequent reviews during the treatment and follow-up periods by the Sponsor Medical Monitor (or appropriately qualified designee) and PPD Medical Monitor (or appropriately qualified designee) throughout the study. Safety data to be reviewed will include selected chemistries, hematology, coagulation, ECG, vital signs and adverse events.

1.7 Data Management

An eCRF utilizing an Electronic Data Capture (EDC) application will be used for this Study.

1.7.1 Case Report Form Data

BioClinica (or designee) is responsible for creating the EDC data entry screens, database and edit checks using definitions developed by Ionis Pharmaceuticals, Inc. Ionis Pharmaceuticals, Inc. is responsible for the review, data management querying and locking of the database.

Data are single-entered into the EDC system by the investigator site staff. Programmed edit checks (computer logic that checks the validity of the data entered and also prompts for missing data that is expected to be entered) are run and automatic queries are generated. Ionis Pharmaceuticals, Inc. reviews all data for accuracy and validity and generates additional queries in the EDC system when necessary. The data are corrected or an explanation concerning the query is provided in the EDC system. After all data are entered, reviewed (by Data Management and Clinical Development) and queried, and all queries resolved, the database is locked.

1.7.2 Laboratory Data

Ionis Pharmaceuticals, Inc. is responsible for the format of the laboratory electronic data transfers, transfer schedule and review of the clinical laboratory data. This lab data will be stored as SAS data sets. Data from BCH may be stored in an Excel spreadsheet.

Immunogenicity results will be available after final database lock.

2.5.3 Pharmacokinetic Data and Immunogenicity (IM) Data

Ionis Pharmaceuticals, Inc. is responsible for the management and review of the PK plasma concentration data and IM data. This process involves reviewing the patient and visit identifiers (i.e., patient demographics) with the clinical data collected in the EDC system. The PK and IM data are not stored in the EDC system.

2 ANALYTICAL PLAN

2.1 General Overview of Analyses

2.1.1 General Statistical Methods

Descriptive summary statistics including number of patients, mean, standard deviation, median, and range (minimum, maximum) for continuous variables, and counts and percentages for categorical variables will be used to summarize most data. All statistical tests will be conducted using 2-sided tests with 5% Type I error rate unless otherwise stated.

PK parameters will be summarized using number of patients, mean, standard deviation, coefficient of variation (CV), geometric mean, median, minimum, and maximum.

All analyses and tabulations will be performed using SAS® Version 9.2 or higher and Phoenix/WinNonlin version 6.1 or higher on a PC platform.

A separate analysis for on-treatment period might be provided if deemed necessary.

Pooled groups:

Patients who are placebo-treated will be pooled and analyzed as a single placebo group.

Patients who are ISIS 416858-treated may be pooled and summarized as the ISIS 416858 total group.

Baseline definition:

Unless otherwise specified, baseline for all safety laboratory results will be defined as the last non-missing measurement prior to the first dose. For post-dialysis Blood Urea Nitrogen (BUN) measures for Urea Reduction Ratio (URR) determination, post-dialysis baseline will be defined as the last non-missing post-dialysis measurement prior to the first dose

Analytical visits:

All post-baseline data will be summarized according to the visit windows in the table below. For patients who have multiple visits within a window, the average will be used in the summary for continuous variable and the worst case result will be used for categorical variable.

Table I Visit window for Clotting

Analysis visit	Visit window
Screening	<1
Baseline	last non-missing measurement prior to the first dose
Day8	[2, 11]
Day 15	[12, 21]
Day29	(22, 35]
Day43	[36, 49]
Day 57	[50, 63]
Day71	[64, 77]
Day 85	[78, 91]
Day99	(92, 105]

Day 113	[106, 116)
Day 120	[117, 126)
Day 134	(127, 140)
Day 148	(141, 154)
Day 162	[155, 168)
Day 176	[169, 182]
Day 190	(183, 196]
Day 204	[197, 210]
Day 218	[211, 224]
Day 232	[225, 238]
Day 246	(239, 252]
Day 260	[253, 266]

Table 2 Visit window for Vital Signs

Analysis visit	Visit window
Baseline	last non-missing measurement prior to the first dose
Day 5	(2, 6)
Day 8	[7, 9]
Day 12	[10, 13]
Day 15	[14, 17]
Day 22	[18, 25)
Day 29	[26, 32)
Day 36	[33, 39)
Day 43	[40, 46]
Day 50	[47, 53]
Day 57	[54, 60]
Day 64	[61, 67]
Day 71	[68, 74]
Day 78	[75, 81)

Day85	[82, 88]
Day92	[89, 95]
Day99	[96, 102]
Day 106	[103, 109]
Day 113	[110, 116]
Day 120	[117, 123]
Day 127	[124, 130]
Day 134	[131, 137]
Day 141	[138, 144]
Day 148	[145, 151]
Day 155	[152, 158)
Day 162	[159, 165]
Day 169	[166, 172]
Day 176 ---	[173, 182]
Day 190	[183, 196)
Day 204	[197, 210]
Day 218	[211, 224]
Day 232	[225, 238]
Day 246	[239, 252]
Day260	[253, 266]

Table 3 Visit window for Electrocardiogram

Analysis visit	Visit window
Baseline	last non-missing measurement prior to the first dose
Day29	[2, 53]
Day78	[54, 126]
Day 176	[127, 217] -
Day260	[218, 273]

Table 4 Visit window for Chemistry panel, Hematology, and Coagulation Panel

Analysis visit	Visit window
Baseline	last non-missing measurement prior to the first dose
Day5	(2, 8]
Day 12	(9, 13]
Day 15	[14, 18]
Day22	[19, 25)
Day29	[26, 32]
Day36	[33, 42]
Day 50	[43, 56]
Day64	[57, 70]
Day78	(71,84]
Day92	[85, 98]
Day 106	[99, 112]
Day 120	[113, 126]
Day 134	[127, 140]
Day 148	(141, 154]
Day 162	[155, 168]
Day 176	[169, 182]
Day 190	[183, 196]
Day 204	[197,210]
Day 218	[211, 224]
Day 232	[225, 238]
Day 246	[239, 252]
Day 260	[253, 266]

Table 5 Visit window for Blood Urea Nitrogen, Post-Dialysis BUN, Urea Reduction Ratio

Analysis visit	Visit window
----------------	--------------

Baseline	last non-missing measurement prior to the first dose
Day36	[2, 49]
Day64	[50, 77]
Day92	[78, 105]
Day 120	[106,133]
Day 148	(134, 161]
Day 176	[162, 189]
Day 204	[190, 217]
Day 232	[218,245]
Day260	[246, 273]

Table 6 Visit window for Inflammatory Markers

Analysis visit	Visit window
Baseline	last non-missing measurement prior to the first dose
Day 15	[2, 21]
Day29	[22, 39]
Day50	[40, 63]
Day78	[64, 91]
Day 106	[92, 119]
Day 134	[120, 147]
Day 162	[148, 168]
Day 176	[169, 189]
Day 204	[190,217]
Day 232	[218, 245]
Day 260	[246,273]

2.J.2 *Populations*

The following populations will be used in this study, and any exclusion of patients from the populations will be documented and decided upon by appropriate medical, clinical, data management, and statistical personnel at Ionis Pharmaceuticals prior to unblinding.

Intent-to-Treat Population (ITT)

All subjects randomized who have received at least 1 dose of Study Drug (ISIS 416858 or placebo). Results will be summarized under the treatment to which patients were randomized.

Per Protocol Population (PPS):

All subjects who are randomized without missing more than 2 doses during the first 12 weeks or more than 5 doses over the 26-week Treatment Period and who do not have any major protocol violations that would affect the interpretation or integrity of the study results.

Safety Population:

All subjects randomized who have received at least 1 dose of Study Drug. Results for Cohorts A and B will be summarized under the treatment to which patients received.

Atrial Fibrillation (AF) Substudy population:

All randomized subjects who were reported at baseline as having a documented history of atrial fibrillation and have received at least 1 dose of Study Drug (ISIS 416858 or placebo).

PK Substudy Population:

All randomized subjects who participated in the PK subgroup and have received at least 1 dose of active Study Drug (ISIS 416858) and had at least 1 PK sample collected and analyzed with evaluable results for ISIS 416858 concentration.

PK Population:

All randomized subjects who have received at least 1 dose of active Study Drug (ISIS 416858) and had at least 1 PK sample collected and analyzed with evaluable results for ISIS 416858 concentration.

Platelet Function/Activation Substudy Population:

All subjects who participated in the Platelets Function/Activation substudy by having at least 1 evaluable sample assessed for flow cytometry and have received at least 1 dose of active Study Drug (ISIS 416858 or placebo).

In addition to the above analysis populations, it is recognized that some data displays will be provided for "All Screened" and "Screening Failures" patients.

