2.3.3.4 AE of Interests

Adverse events of interest additionally include the following categories from CRFs:

- Cerebrovascular Accident/Transient Ischemic Attack
- Coronary Ischemia
- Venous Thromboembolism

AE listing will be provided for each AESI category including the seriousness of the AE.

2.3.4 *Laboratory Measurements*

The following is the list of routine lab analytes that may be collected throughout the study:

- Chemistry: Total protein, Albumin, Glucose, Blood urea nitrogen (BUN) for urea reduction ratio (URR) determination, Total bilirubin, Direct bilirubin, Indirect bilirubin, ALT, AST, GGT
- Hematology: Red blood cells, Hemoglobin, Hematocrit, MCV, MCH, MCHC, Platelets, Mean Platelet Volume, WBC, and WBC differential (percentage and absolute) (Basophils, Eosinophils, Lymphocytes, Monocytes, and Neutrophils)
- Inflammatory Markers: Hs-CRP, D-climer, Beta-2-M, Cardiac troponin I and T, NT-proBNP
- Screening Tests: Hepatitis B surface antigen, Hepatitis C antibody, HIV antibody, FSH (women only, if applicable) and Serum PhCG (women only). This data will only be displayed in patient listings.

Missing WBC differential absolute counts and percentages will be derived as needed:

If WBC differential absolute counts are missing, and percentages are available, then absolute counts will be calculated by multiplying the percentage by total WBC count. Conversely, if absolute count is available, and percentage is missing, then percentage will be calculated by dividing absolute count by the total WBC count. If neutrophils counts and percentages are missing, and segmented neutrophil and band neutrophil results are available, then neutrophils will be calculated by adding segmented neutrophils and band neutrophils.

Chemistry and hematology panel results, change and percent change from baseline will be summarized by treatment group and study visit.

For ALT and AST, the number and percent of patients falling in each of the following categories for central laboratory data will be tabulated by treatment group:

- Confirmed ALT \geq 3x ULN
- Confirmed ALT \geq 5x ULN
- Confirmed AST \geq 3x ULN
- Confirmed AST \geq 5x ULN

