8.6.2 Stopping Rule for Platelet Count Reduction

In the event of a confirmed platelet count less than $75,000/\text{mm}^3$, dosing of a subject with Study Drng (ISIS 416858 or placebo) will be stopped permanently. From the first, additional laboratory investigations will be conducted as outlined in [Table 4](#). The platelet count should be tested weekly until it is above $100,000/\text{mm}^3$. The subsequent follow-up schedule for any events meeting this stopping criterion will be determined by the Investigator in consultation with the Sponsor Medical Monitor (or designee).

In the event of a platelet count $< 50,000/\text{mm}^3$, the Sponsor must be notified within 24 hours and platelets are to be monitored daily until 2 successive values show improvement, then monitored every 2-3 days until the platelet count is stable. A stable platelet count is considered when at least 6 consecutive values measured are $> 100,000/\text{mm}^3$ with no downward trend as determined by the Sponsor Medical Monitor (or designee). It is recommended that the subject receive glucocorticoid therapy to accelerate the recovery in the platelet decline (strongly recommended if platelet count $< 25,000/\text{mm}^3$). To optimize patient treatment, a discussion between the Investigator and the Sponsor Medical Monitor (or designee) must occur. Treatment guidelines for immune thrombocytopenia ([Provan et al. 2010](#)) recommend dexamethasone 40 mg daily for 4 days every 2-4 weeks for 1-4 cycles; prednisolone 0.5-2 mg/kg/day for 2-4 weeks then taper; or methylprednisolone 30 mg/kg/day for 7 days (**note:** may require continuation with oral corticosteroids after methylprednisolone).

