10.6.2 Safety Analysis

Treatment duration and amount of Study Drng (ISIS 416858 or placebo) received will be summarized by treatment group. Subject incidence rates of all AEs will be tabulated by the Medical Dictionary for Regulatory Activities (MedDRA™) system organ class, and by MedDRA™ term. Tables and/or narratives of treatment-emergent deaths, serious and significant AEs, including early withdrawals due to AEs, will also be provided.

All treatment-emergent AEs, all treatment-emergent AEs potentially related to Study Drng, all treatment-emergent serious AEs, and all treatment-emergent serious AEs potentially related to Study Drng (ISIS 416858 or placebo) will be summarized.

Laboratory tests to ensure subject safety including chemistly panel, complete blood count with differential, coagulation panel, complement etc., will be summarized by study visits for each treatment group. These safety variables will also be presented as change and percent change from Baseline over time after Study Drng (ISIS 416858 or placebo) administration, as appropriate.

Vital sign and ECG measures will be tabulated by treatment group. In addition, the number of subjects who experience abnormalities in clinical laboratory evaluations will be summarized by treatment group.

Incidence of bleeding events including the following will be tabulated by treatment:

- MB
- CRNMB
- Minor bleeding
- Combination of MB and CRNMB

Physical examination data will be provided in the data listing. Concomitant medications will be coded using World Health Organization (WHO) Drng dictionruy and summarized by treatment, ATC class and generic name.

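### By-visit platelet summaries average a low count with the retests it triggers, and the SAP has no by-arm table of lowest or below-threshold platelet counts

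*Combined protocol and SAP*

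**What the plan says.** SAP 2.1.1 assigns all post-baseline data to analysis windows. Where several results fall in one window, "For patients who have multiple visits within a window, the average will be used in the summary for continuous variable", whereas "the worst case result will be used for categorical variable". The hematology windows stand under "Table 4 Visit window for Chemistry panel, Hematology, and Coagulation Panel": 5 to 10 days wide up to the Day 36 window, and 14 days wide from the Day 50 window on.

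SAP 2.3.4 plans this for platelets: "Chemistry and hematology panel results, change and percent change from baseline will be summarized by treatment group and study visit". The statistics are those of SAP 2.1.1: "Descriptive summary statistics including number of patients, mean, standard deviation, median, and range (minimum, maximum) for continuous variables". The only laboratory threshold table is introduced by "For ALT and AST, the number and percent of patients falling in each of the following categories", at 3 and 5 times ULN. Patients who meet safety monitoring or stopping rules are to be listed.

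The protocol calls for routine platelet counts every 2 weeks (6.1.3) and weekly counts at 100,000/mm³ or less (8.5.2). Below 50,000/mm³, "platelets are to be monitored daily until 2 successive values show improvement", and then every 2 to 3 days until stable (8.6.2). Protocol 10.6.2 adds that "the number of subjects who experience abnormalities in clinical laboratory evaluations will be summarized by treatment group".

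**The concern.** The amount of averaging depends on the outcome. Each Table 4 window holds one nominal day, so a patient with unremarkable counts usually contributes a single value. A patient whose count falls contributes the low value plus the retests that it triggered, and the testing becomes more frequent below 50,000/mm³. Averaging therefore acts mostly on the patients of most interest.

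The table's minimum does not rescue this, because it is a minimum over patients' window averages. The worst-case rule does not help either: it covers categorical variables, and the SAP defines no platelet category.

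The stake is the by-dose description of a named risk. Protocol 2.5 cites severe thrombocytopenia in 4 of 32 monkeys in the higher-dose groups, and Grade 4 events in patients given two related drugs above 200 mg per week. This trial gives 200, 250 and 300 mg weekly, safety is part of its primary objective, and platelets have their own stopping rule. A reader of the planned tables could not find how many patients per arm fell below 100,000, 75,000 or 50,000/mm³.

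**Working it through.** The documents give no platelet rate or power figure on this point, so there is nothing to reproduce. The check is arithmetic on the averaging rule. Counts are in thousand/mm³.

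**1. How often averaging applies.** Each of the 22 post-baseline windows in Table 4 contains exactly one nominal analysis day. Averaging therefore acts mainly on unscheduled or shifted tests. Results on the same day are not averaged: the confirmation paragraph of SAP 2.3.4 takes the worst.

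**2. One low count and one retest in the same window.** Mean = (low + retest)/2.
- (70 + 150)/2 = 110
- (45 + 150)/2 = 97.5
- (45 + 110)/2 = 77.5
- (20 + 150)/2 = 85
- (20 + 110)/2 = 65

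The first four lie above the stopping level of 75; the last does not.

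**3. Protocol retest cadence below 50.** Inputs from the documents: window [99, 112]; daily tests until two successive improvements, then every 2 or 3 days. Assumptions: nadir 45; linear recovery of 5, 10 or 20 per day; a ceiling of 180; improvement from the first retest. The documents give no recovery speed.

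Worked case, nadir on Day 99, 5 per day, 2-day spacing (Days 99, 100, 101, 103, 105, 107, 109, 111): (45 + 50 + 55 + 65 + 75 + 85 + 95 + 105)/8 = 575/8 = 71.9.

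Window means, shown as 2-day / 3-day spacing:

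| Day nadir found | 5 per day | 10 per day | 20 per day |
|---|---|---|---|
| 99 (start of window) | 71.9 / 67.5 | 98.8 / 90.0 | 128.1 / 116.7 |
| 103 (earliest scheduled draw, 3-day visit window) | 62.5 / 61.0 | 80.0 / 77.0 | 110.8 / 104.0 |
| 106 (nominal day) | 58.0 / 55.0 | 71.0 / 65.0 | 97.0 / 85.0 |

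A nadir of 20 on Day 99 with 2-day spacing gives 46.9, 73.8 and 112.5. In every cell the nadir is replaced by a higher value. Whether that value crosses 75 or 100 depends on recovery speed and on where in the window the nadir falls.

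**4. Effect on the arm mean.** 204/3 = 68 per cohort, and 68 × 3/4 = 51 per active dose; pooled placebo is 3 × 17 = 51. Moving one patient from 45 to 72 shifts an arm mean by 27/51 = 0.5; from 45 to 128, by 83/51 = 1.6. Both are negligible.

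**5. What a by-arm count would show.** Exact (Clopper-Pearson) 95% limits with n = 51:
- 0/51: 0 to 7.0%
- 1/51: 0.05 to 10.4%
- 3/51: 1.2 to 16.2%

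**The case against.** The strongest reply is that no patient with a serious drop is lost. A reader might infer that averaging defeats the protocol's platelet rules; the documents do not support that. Protocol 6.1.3, 8.5.2 and 8.6.2 act on individual results as they arrive, and the SAP averaging rule touches none of them. Everyone who meets a monitoring or stopping rule is listed. SAP 2.3.3 tabulates by arm the adverse events by maximum severity and those leading to permanent discontinuation, and protocol Appendix D grades platelet decreases at 75,000 and 50,000/mm³.

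This stands as far as individual cases go. It does not supply a rate by arm. A listing has no denominators or intervals. Under protocol 9.5.1 a laboratory value becomes an adverse event only on the investigator's judgement. Appendix D runs its mild grade from LLN down to 75,000 and puts everything below 50,000 in one grade, so neither 100,000 nor 25,000 can be read from it.

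A reader might also infer that by-visit means are materially biased toward no effect, or that all retests fall in one window after drug is stopped. Neither follows. The shift in means is trivial (step 4). Windows are shorter before Day 43, and follow-up below 50,000 can run into later windows. Patients between 75,000 and 100,000 are retested weekly without meeting the platelet stopping rule.

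Finally, the averaging sentence speaks of visits, so one could argue that unscheduled tests are left out. The SAP does not say so. On that reading a nadir found on an unscheduled test would be absent from the by-visit table altogether.

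**Conclusion.** The point holds as a reporting gap. By-visit platelet summaries lose the nadir whenever a higher result from another day shares its window. The loss shows chiefly in the displayed minimum and hardly at all in arm means. More important, the SAP specifies no by-arm table of lowest or below-threshold platelet counts, so the protocol 10.6.2 commitment is not carried out for a named risk.

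For a nadir of 45 thousand/mm³ the value entered is about 72 to 128 at the start of a 14-day window with 2-day retests (68 to 117 with 3-day retests), and 55 to 97 on the nominal day. These ranges rest on assumed linear recovery of 5 to 20 per day. With slow recovery the average stays below 75, so the distortion can be large but is not universal. Nothing here suggests that cases go undetected during the trial or are missing from the report. The change is a cheap improvement worth making.

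**What to change.** Keep the by-visit summaries. Add to SAP 2.3.4 one table by treatment group, with the ISIS 416858 total, showing:

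- each patient's lowest post-baseline platelet count, summarized descriptively;
- the number and percent of patients at or below 100,000/mm³, and below 75,000, 50,000 and 25,000/mm³, with exact 95% intervals.

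Use all scheduled and unscheduled results. Show the counts both unconfirmed and confirmed under the SAP's existing 7-day rule; that rule takes the retest's category when the retest is better, so the two can differ. Restricting the table to scheduled-visit values would not serve, since it can discard a nadir found on an unscheduled test.

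The cost is a short SAP addition and one table from data already collected. The drawback is that patients tested more often have more chances to show a low value; a footnote giving the number of platelet results per patient by arm would let the reader judge this. No clinical rule changes.
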